The study is scheduled to last 24th months. Baseline clinical observation will be done 30 days after placement of adhesion restoration (First data research); a second appointment after 12th months (second data; data not to be included on final report, according to the main purpose and trial hypothesis to study) and the last research evaluation will be at 24th months after baseline (Final data/report). Clinical trial may continue for similar assessment intervals, after 24th months evaluation. This situation requires new analysis according to the clinical and economics conditions, at that time.

2.2- POPULATION AND PARTICIPANT SELECTION

All participants will be informed (Written and verbal Inform Consent, Annex 1) about the trial conditions and purposes, but will not be aware of what tooth will received the adhesion treatment strategy under evaluation. Written informed consent form (Annex 1), according to World Medical Association Declaration of Helsink (31), will be obtained from all participants prior to starting the treatment. University

Ethics Committee review and approved the present protocol. This clinical trial is done according to the European Union law for clinical research and National Law for Clinical Research (Law 21/2014, of 16 April), and was analysed, approved and authorized by the National Competent Authorities

- **CNPD**, Portuguese Data Protection Authority (Authorization and registry 6430/2015 at 7 July 2015; Case 2536/2015).
- **CEIC**, National Ethics Committee for Clinical Research (N.º 20150305; Approved at 3th August 2015)
- INFARMED, National Authority of Medicines and Health Products, IP (N.° EC/011/2015; DPS/DM/450.10.053/2015/0314; Authorization at 4th August 2015)

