In this study will be included participants with clinical diagnosis of tooth structure coronal loss and needs for cervical (vestibular surface) restoration without chemical or bacterial origin, called non-carious cervical lesion (NCCL) located in pre-molars/molars (PM/M) teeth, with cavity dimensions defined in the study design. Therefore, restorations can be made in PM or M teeth; a participant can have up to 16 teeth (8PM + 8M) with NCCL. The number of teeth to restore by participant will be of maximum of 6 and a minimum of one NCCL, within this clinical trial. The allocation of the study arms (G1 to G6) to a particular tooth is randomly allocated, with the information available to the operator/principal investigator in sealed envelopes and previously prepared by the investigator-statistics. The allocation of the study arms (G1, G2, G3, G4, G5, G6) to each tooth by participant is performed randomly, but ensuring that the distribution of the groups is not repeated in the same participant. For this purpose, will be organized by the statistical investigator, 210 envelopes with 35 sequences of 6 study arms, where in each order of 6 groups is randomized.

If the patient has more than six teeth that meet the inclusion criteria, the selection of the PM and M teeth to be included in the clinical trial will be conducted randomly by scenarios randomized by the statistical investigator after participation and contact for the effect (not done a priori, since it is necessary 19448 scenarios prior randomization before observing any patient, whereas the possible teeth to be selected for treatment is between 6 and 16 and the teeth to select from 6).

The participant has as cost the academic/scientific fees, as in usual clinical context of Dentistry School Clinic of **Sector Sector** as "restoration of a tooth surface"/ by tooth to restore (One to six teeth), which of course would have to make even not participating in the investigation, as the Dentistry School Clinic fee scale.

The restorations included in this trial will be evaluated for determine clinical performance from baseline to 24th month by the three calibrated examiners. These observation appointments (three, in two years) as part of the clinical trial will be free of charges for participants. Baseline and 24th month data will be statistically analysing, according to this trial purpose and hypothesis.

2.3-STUDY ADHESION ARMS

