One week, before the Restorative procedure (1st appointment): Inform the patient (Written/Verbal- Anexx-1); Patient signature of informed consent; Fulfilment of the project clinical file (patient identification, general clinical summary, oral clinic examination, oral hygiene state; Annex 2); Dental prophylaxis with fluoride toothpaste and water with a nylon brush. Vitality tests (cold and hot) executed with spray *Endo cool* (ethyl chloride) and warm instrument; Pre-operative sensitivity evaluation by applying air for 10 seconds from a dental syringe placed 2 cm from the tooth surface (16); NCCLs cavities will be evaluated according to the degree (1, 2, 3, 4) of sclerotic dentin (32), cavity dimensions (H-height, W-width, and D-depth) in millimetres (mm) and geometry (evaluated by profile photograph, as Angles Acute (A), Severe (S), Obtuse (O) (16);

1st Appointment-Intervention: Initial intra-oral/cavity surface and tooth digital photography; Teeth anaesthesia with 3% mepivacaine (Scandinibsa, Sintra Business Park, Portugal); Operatory field isolation with cotton rolls and retraction floss (Ultradent)._All cavities cleaned with pumice and water in a rubber cup, followed by rinsing and drying. Selection composite colour by shade guide; Adhesive interventions according to G1 to G6 arms assignment. Adhesive systems will be used as SingleDose mode. Composite restorations (AdmiraFusion Universal nano-hybrid composite) with incremental filling technique (two increments maximum), light-cured (LED Unit) with an intensity of 1000mW/cm2, during 40 seconds. Restorations will be finished immediately with diamond disks (OptiDisc® medium 40μm; Kerr) and burns. Polishing performed with diamond-impregnated silicone polishers (Dimanto, Voco, CuxHaven) during 10 seconds._Intra-oral digital photography of the restoration.

2.6-CLINICAL RECALL

Baseline (30 days after restoration), 12th and 24th months Appointments

1 - Intra-oral digital photography of the NCCL restoration;

2- Pos-operative sensitivity evaluation by applying air for 10 seconds from a dental syringe placed 2 cm from the tooth surface (16);

3 – Clinical direct evaluation by 3 calibrated examiners according to FDI (33) (Annex 3) and USPHS (34) (Annex 4);

4°- Data register.

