Study variable definition_- Clinical/direct observation and performance evaluation acceptance by means of FDI (*FDI World Dental Federation - clinical criteria for the evaluation of direct restorations*) (Adapted from (33) (Annex 3) and USPHS (34) (Annex 4).

2.7- DATA AND STATISTICAL ANALISYS PLAN (SAP)

Data statistical analysis and description according to aims of this trial; Specific program for statistical data analysis (IBM(c) SPSS(c) Statistics vs. 22 or later) will be used. The changes in parameters clinical performance (paired comparison analysis) by both, FDI and USPHS criteria will be assessed by McNemar or Wilcoxon tests, for both

primary and secondary outcomes, to determine differences between treatments with regard to aesthetic, functional and biological parameters from baseline to 24th month recall (longitudinal assessment). Differences will be considered to be significant at P<0.05. Whenever 3 groups will be compared at 24 months' recall, a Kruskal Wallis test will be used and upon significant differences detection, then Mann-Whitney tests considering Bonferroni correction will be used for pairwise group comparisons.

Comparison of FDI and USPHS acceptance (success rate) criteria evaluation outcomes for Esthetic, for Functional and for Biological Parameters, at 24th Month Follow-up, were compared using the chi-square test.

If missing data occurs, that is, if dropouts or non-observed due to loss of retention of the restoration, then the paired comparison will consider for the baseline just the restorations existing at the last moment (24 months).

2.8- OBSERVATIONS REGARDING SAMPLE CALCULATION

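### The 12-month examination is kept out of the final analysis, so a restoration's known 12-month retention status has no route into the retention comparison if the participant misses the 24-month visit

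*Combined protocol and SAP*

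**What the plan says.** Section 2.6 lists the recall visits as "Baseline (30 days after restoration), 12th and 24th months Appointments". The same work is set for each: a photograph, the air sensitivity test, and direct scoring on both scales by three calibrated examiners.

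Section 2.1 describes the 12-month results as "data not to be included on final report, according to the main purpose and trial hypothesis to study". Section 2.2 agrees: "Baseline and 24th month data will be statistically analysing, according to this trial purpose and hypothesis".

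Retention rate is the subject of three of the null hypotheses: G1 against G4 and G6, G2 against G3 and G5, and the comparison of the three adhesives.

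Section 2.7 compares three groups at the 24-month recall with Kruskal-Wallis and then Mann-Whitney tests. It names no time-to-loss method. Its one missing-data rule applies "if dropouts or non-observed due to loss of retention of the restoration", in which case "the paired comparison will consider for the baseline just the restorations existing at the last moment (24 months"). The rule is worded for the paired comparison. The denominator for retention rates is not defined in that section or elsewhere.

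**The concern.** Once a trial restoration is recorded as lost at 12 months, its 24-month retention outcome is settled. The reason given for leaving out the 12-month data is that the trial asks a 24-month question, but for retention the 12-month record helps to answer that question. A restoration seen intact at 12 months and not seen again is also informative, because it survived the first of the two intervals.

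Under the plan, neither record has a route into the retention comparison when the participant is absent at 24 months. Participants carry one to six trial restorations, so one absence can remove up to six at once. What is at stake is precision in arms of 35 and, if absence is linked to failure, the retention estimates and the differences between arms.

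**Working it through.** The plan states no figure on this point that could be reproduced, and no failure, dropout or power assumption. Its total checks: 6 × 35 = 210 restorations. All rates below are assumptions for illustration.

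**Inputs**
- n = 35 per arm, 210 in total (sections 2.2, 2.3 and 2.8).
- f1 = proportion lost by month 12, assumed 5-15%.
- f2 = proportion of the rest lost between months 12 and 24, assumed 5%.
- aF, aI = proportion unseen at 24 months among restorations lost, or intact, at month 12 (assumed). All are taken to have been examined at month 12.

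**Formulas**
- True 24-month retention = (1 − f1)(1 − f2).
- Retention among those seen at 24 months = (1 − f1)(1 − aI)(1 − f2) / [(1 − f1)(1 − aI) + f1(1 − aF)]. This counts a lost restoration as a failure when its owner attends, which is a favourable reading of the plan.
- Known failures not counted = n × f1 × aF.

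**Step 1: absence unrelated to 12-month status**
- Restorations with unused 12-month data: 210 × 0.10 = 21, to 210 × 0.20 = 42.
- Known failures not counted: 210 × 0.05 × 0.10 = 1.05, to 210 × 0.10 × 0.20 = 4.2, over six arms. Per arm: 1.05/6 = 0.2, to 4.2/6 = 0.7.
- Bias, with f1 = 10% and both absence rates 20%: 0.90 × 0.80 × 0.95 / (0.90 × 0.80 + 0.10 × 0.80) = 0.684/0.80 = 85.5%. The truth is 0.90 × 0.95 = 85.5%, so there is no bias.
- The cost is information. Each arm is analysed on 35 × 0.80 = 28 to 35 × 0.90 = 31.5 restorations, although first-interval loss is known for all 35.

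**Step 2: absence more common after a failure**

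| f1 | aF | aI | True | Among those seen | Overstatement |
|---|---|---|---|---|---|
| 5% | 30% | 10% | 90.2% | 0.81225/0.890 = 91.3% | 1.0 points |
| 10% | 50% | 10% | 85.5% | 0.7695/0.860 = 89.5% | 4.0 points |
| 15% | 60% | 20% | 80.7% | 0.646/0.740 = 87.3% | 6.5 points |

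The first and last rows are the extremes of the scenarios tried (f1 5-15%, aF 30-60%, aI 10-20%).

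For two arms with f1 of 5% and 15%, the true difference is 0.9025 − 0.8075 = 9.5 points. With absence of 50% against 10%, those seen show 0.81225/0.880 − 0.72675/0.840 = 0.923 − 0.865 = 5.8 points. With 60% against 20%, they show 0.722/0.780 − 0.646/0.740 = 0.926 − 0.873 = 5.3 points.

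**Step 3: does using the 12-month data help?**
- A two-interval life table takes first-interval retention from everyone seen at month 12 (1 − f1). It takes second-interval retention from those intact at month 12 and seen at month 24 (1 − f2). The product is the true value in every scenario above, provided that, given 12-month status, absence at 24 months is unrelated to later loss.
- Adding back only the absentees' failures does not work. With f1 = 10% and 20% absence in both groups, it gives 0.684/(0.72 + 0.10) = 83.4% against a true 85.5%, which is too low.

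**The case against.** A fixed 24-month endpoint is legitimate, the two-visit analysis was declared in advance, and no hypothesis asks when failures occur. That stands: leaving timing undescribed is not a fault here, and the fix keeps the 24-month target.

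A reader might infer that the plan necessarily inflates retention because known failures are dropped. The documents do not support this. An absentee leaves both numerator and denominator, so the estimate among those seen shifts only if absence is related to 12-month status, and the plan has no information on that. A reader might also price each uncounted failure at 1/35 = 2.9 points. That is wrong for two reasons: the absentee is no longer in the denominator of 35, and the 1-4 failures are spread over six arms.

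It can also be said that no sentence removes these failures from the retention rate. Indeed, the section 2.7 rule covers only the paired comparison, and the retention denominator is undefined. The absence of a route is an inference from sections 2.1 and 2.2 together, but those sections leave no other reading for the 12-month data. Restorations lost by month 12 in participants who do attend at 24 months can still be scored as missing then, so the point is confined to absentees.

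Two further replies carry less weight. Section 2.9 has performance-related events reported to the authorities at the final evaluation, but that is safety reporting and does not enter the arm comparison. The point also overlaps with the section 2.7 missing-data rule. Yet correcting that rule for losses seen at 24 months would not by itself admit the 12-month records.

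**Conclusion.** The point holds as a weakness in the analysis plan that is worth correcting at low cost. Retention status is recorded at 12 months, and the plan gives it no way to inform the retention comparison for participants absent at 24 months.

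If absence is unrelated to 12-month status, the consequence is lost precision only. If participants with a failure are absent more often, retention is overstated (1.0 to 6.5 points in the assumed scenarios) and true differences between arms can shrink. Such a link is plausible but not shown by the documents, so the bias must be stated as conditional. Every magnitude rests on assumed failure and absence rates.

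**What to change.** Amend sections 2.1, 2.2 and 2.7 so that the 12-month retention data enter the final analysis and report:

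- Keep 24-month retention as the estimate of interest. Estimate and compare it with a life-table or discrete-time analysis over two intervals, baseline to 12 months and 12 to 24 months.
- Count a loss recorded at 12 months as a failure. Let restorations intact at 12 months and then unseen contribute to the first interval. Do both, since adding only the failures biases retention downwards.
- Use standard errors that allow for clustering of restorations within participant.
- State the denominator for each retention rate, and report by arm how many restorations were seen, lost and unseen at each visit.
- State the assumption that, given 12-month status, absence at 24 months is unrelated to later loss.

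Modelling the ordinal FDI and USPHS items over all visits is optional. With about 210 × 0.05 = 10 to 210 × 0.10 = 21 losses by month 12 over six arms on the assumed rates, clustered interval-censored models or a repeated-measures model for each item may be unstable, so the simple retention analysis is enough.

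The cost is changed wording and some extra analysis work. The 12-month visit is already scheduled, so no further data collection is needed.

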The decision to participate in this study is voluntary (Annex 1) as well as the decision to refuse participation and decision of withdrawal of the same, at any time of the study respecting all the rights of the patient/participant. Given the purpose of this study, and the fact of existing multiple and several market therapeutic alternative for this type of interventions, the fact of participate in this study will not involve any additional cost, except the one described in the fee schedule of Dentistry School Clinic . They will not be granted any incentives or financial benefits (payment of travel or counter-parties) to participate in the trial. The participant has as cost the "restoration of the tooth surface, which of course would have to make even not participating in this investigation, as regulated for the clinical practice. The clinical observations, temporarily established (3 appointments in 24th month) to observe participants and evaluate the research restorations performance, will be free of charge for the participants. All other acts that the participant needs or intends to perform, not included in the protocol of this trial, should meet the same, the fees charges of Dentistry School Clinicrestorations are applied to tooth surfaces requiring intervention/repair for the maintenance of dental structure in oral cavity of the patient. The operator (Dentist and

Associate Professor of **Construction**) inform the patient/participant in all aspects related to the study. Refusal of patient participation, the participant's withdrawal and revocation of consent to participate in this study are rights of the patient/participant, without any consequences or reprisal, and without interference in the relationship between users and teachers/researchers/ University and clinical entities.

Patients with ages of 18 up to 65 years which voluntary come to Dentistry School Clinic

of will be recruited in the order in which they are report for appointment, thus forming a convenience sample. According to assessed eligibility (inclusion and exclusion) criteria, volunteers will be selected for this study as recommended, by CONSORT guidelines (30). A minimum of 210 restorations will be performed, randomized in order to be allocated to six interventions, named as adhesion intervention groups (Table 1).

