For the operator calibration procedure, operator will do one restoration of each group in order to identify all steps involved in the application technique. This procedure will be done three times, with one week, interval. All restorations done by the same calibrated operator. Three experienced and calibrated dentists, not involved with the restoring procedures and therefore blinded to the group assignment, will perform the clinical evaluation. For training purposes, the examiners observed 10 photographs that were representative of each score for each criterion, in 10 cervical restorations (not included in this trial), each one, on two consecutive days. An intra-examiner and inter-examiner agreement will be calculated.

Medical devices composition according to manufactures, Voco and Ivoclar Vivadent safety data sheets for adhesives and products is show in Table 2.

safety data sheet).	
Medical Device	Composition
(manufacture)	
Lot#Number	
Futurabond [®] DC (FBDC)	Liquid 1. Acidic adhesive monomer*; BIS-GMA (5-10%), 2-HEMA (5-10%);
(Voco, Cuxhaven, Germany)	Liquid 2. Ethanol (50-100%); Initiator (2.5-5%)
Lot# 1532592	Mixture. organic acids, BIS-GMA, 2-HEMA, TMPTMA, campherchinon,
	amines (DABE), BHT, catalysts, fluorides and ethanol
	pH-value 1.5
Futurabond [®] U (FBU)	Liquid 1. (2-HEMA) (25-50%); BIS-GMA (25-50%); HEDMA (10-25%);
(Voco, Cuxhaven, Germany)	Acidic adhesive monomer (5-10%)*; UDMA (5-10%); catalysts ($\leq 2.5\%$),
Lot# 1543141	silica nanoparticles;
	Liquid 2. Ethanol (50-100%); Initiator (2.5-5%); catalysts (≤ 2.5)
	pH-value 2.3
Vococid®	35% orthophosphoric acid
(Voco, Cuxhaven, Germany)	
Lot# 152135	
Adhese® Universal (ADU)	Liquid: 2-HEMA (10-<25%); Bis-GMA (10-<25%); ethanol (10-<25%); 1,10-
(Ivoclar Vivadent AG,	decandiol dimethacrylate (3-<10%); Methacrylated phosphoric acid ester (3-
Liechtenstein)	<10%); campherquinone (1-<2.5%); 2-dimethylaminoethyl methacrylate (1-
Lot# U35131	<2.5%); 2-dimethylaminoethyl methacrylate (0.1-<2.5%).
	pH-value 2.5-3.0
Admira [®] Fusion	Nano-hybrid ORMOCER®s (organically modified ceramics); large and
(Voco, Cuxhaven, Germany)	precondensed molecules of an inorganic matrix with a high degree of cross-
Lot# (Shade A1, A2, A3, A3,5)	linking. 84 % w/w inorganic fillers. Silicon oxide forms the chemical base, not
1508270, 150827, 1510508,	only for the fillers (nanofillers as well as glass ceramics) but also for the resin
1509381	matrix.

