It was assumed that the minimum number of adhesive restorations to be held in each of the six arms (G1 to G6) is 35 (210 restorations). The researchers did not have detailed information that allows the estimation of the sample size based on power analysis (the effect of the expected difference to the end of the time considered for the study). Thus, in principle they assumed the rules of thumb, usually considered in research situations where there is no advance information concerning the performance evaluation of these adhesive medical devices available on the market, using this assay. Moreover, when considering a "simple" analysis comparison using a McNemar test (repeated measures) in six groups would be necessary in total, including at least 80 cases (to restore teeth) in the sample. When considering at least 35 restorations by group, researchers are greatly increasing the minimum number stipulated in the aforementioned technique. In addition, clinical studies previously performed on this issue (between 2004 and 2012) relative to the post-market clinical evaluation performance of adhesive products/use mode in NCCLs, in the context of restorative dentistry field, has enabled to measure a minimum of 30 restorations as viable for determining events in a short/mean-term as the clinical performance evaluation of a similar nature of adhesives.

2.9- GOOD CLINICAL PRACTICE FOR CLINICAL RESEARCH

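### Fixed sequences of six, available to the only operator, make later arms in a sequence partly predictable and the last one certain

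*Combined protocol and SAP*

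**What the plan says.** Section 2.2 allocates arms G1 to G6 to individual teeth, "with the information available to the operator/principal investigator in sealed envelopes and previously prepared by the investigator-statistics". The list is described as "210 envelopes with 35 sequences of 6 study arms, where in each order of 6 groups is randomized". A participant may contribute one to six lesions, with allocation "ensuring that the distribution of the groups is not repeated in the same participant". The trial size is given in the same section: "A minimum of 210 restorations will be performed, randomized in order to be allocated to six interventions". Section 2.8 repeats it as a minimum of 35 per arm.

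Section 2.4 states "All restorations done by the same calibrated operator". It describes the three examiners as blinded, but not the operator. Table 1 in section 2.3 shows that the arms differ in mixing, etching and rinsing, so whoever places a restoration knows its arm. Section 2.2 also has the operator "inform the patient/participant in all aspects related to the study".

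Three features offer some protection. Someone other than the operator prepares the envelopes. Patients are taken in order of presentation. Where more than six teeth qualify, the teeth are chosen "by scenarios randomized by the statistical investigator after participation and contact for the effect".

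The text does not say when envelopes are opened, whether the included teeth are recorded first, which tooth takes which envelope, what happens to the unused envelopes of a sequence, or who screens and enrols.

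**The concern.** Concealment requires that whoever can influence which participant or lesion enters next cannot tell which arm comes next. Here the list consists of permuted blocks of one fixed size, the size is printed in the protocol, and the one person who sees every assignment also has the envelopes. After a few lesions in a sequence, the remaining arms follow by elimination.

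Under section 2.5, dentin sclerosis, cavity dimensions and geometry are recorded before the restorative visit, so lesion difficulty is visible before allocation. If the coming arm is known or likely, harder lesions can drift towards or away from etched arms or a given product, even without intent. Blinded examiners cannot correct a selection made at entry. The tests in section 2.7 (McNemar, Wilcoxon, Kruskal-Wallis, Mann-Whitney, chi-square) do not adjust for lesion characteristics.

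**Working it through.** **Inputs.** Six arms, 35 sequences, each arm once per sequence, one to six lesions per participant (section 2.2); 35 restorations per arm as a minimum (section 2.8). Arms with an acid-etching step are G2, G3 and G5; arms without are G1, G4 and G6 (Table 1).

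**The plan's own figure.** 35 × 6 = 210, which reproduces. Since 210 is a minimum, the list has no spare envelopes.

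**Guessing the arm.** At position k of a sequence, 7 − k arms remain, so the best guess is right with probability 1/(7 − k).

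| Position | 1 | 2 | 3 | 4 | 5 | 6 |
|---|---|---|---|---|---|---|
| Arm guessed correctly | 16.7% | 20% | 25% | 33.3% | 50% | 100% |
| Mode guessed correctly | 50% | 60% | 60% | 70% | 70% | 100% |

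- Arm: 1/6 + 1/5 + 1/4 + 1/3 + 1/2 + 1 = 2.45; 2.45/6 = 40.8%, or 35 × 2.45 = 85.75 of 210. Simple randomisation would give 1/6 = 16.7%, or 35 of 210.
- The arm is certain at position 6 only: 1/6 of envelopes, 35 of 210 if all are used.

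**Guessing the mode.** Each sequence has three etched and three unetched arms, and the best guess is the mode with more arms left.

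- Correct guesses: 0.5 + 0.6 + 0.6 + 0.7 + 0.7 + 1 = 4.1; 4.1/6 = 68.3%, against 50% by chance.
- The mode is certain with probability 0.1 at position 4, 0.4 at position 5 and 1 at position 6: 1.5/6 = 25%, or 52.5 of 210.

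**Does this reach a new participant's first lesion?** The plan allows two readings.

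1. *Part-used sequences carry over.* This is an inference from the numbers. With a fresh sequence per participant and leftovers discarded, 35 sequences give 35 × (mean lesions) restorations: 35 × 6 = 210 only if all 35 participants have six lesions, and 35 × 3 = 105 if the mean is three (an assumed value). If envelopes then run strictly in order, the first arm of a new participant can be guessed about 41% of the time (assumed lesion counts: all one, uniform 1–3, or uniform 1–6). Strict order, however, conflicts with the rule against repeating an arm within a participant. Averaged over the six starting positions, the chance of a repeat is 2.8% for two teeth, 11% for three, 27% for four, 49% for five and 75% for six. A compliant procedure must therefore depart from strict order, and the plan does not say how.
2. *Each participant starts a new sequence.* The first arm is then unpredictable (1/6). Later lesions are not. With lesion counts 1 to 6 equally frequent (an assumption), expected correct guesses are 0.167 + 0.367 + 0.617 + 0.95 + 1.45 + 2.45 = 6.0 over 1 + 2 + 3 + 4 + 5 + 6 = 21 lesions, or 28.6%. A sixth lesion's arm is certain.

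On the second reading the exposure is which tooth takes the next envelope and whether a further lesion is entered, because nothing requires the included teeth to be fixed before envelopes are opened.

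**The case against.** The best defence is that the envelopes are sealed and prepared by someone else, patients come in order of presentation, and teeth above six are selected at random. Lesion characteristics are also recorded before treatment, so imbalance between arms could be checked afterwards. These points stand as partial safeguards. Order of presentation does not govern how many lesions are entered or in what order they take envelopes, the random tooth selection applies only above six eligible teeth, and a later check can reveal imbalance without preventing it.

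A second objection is that carry-over is nowhere stated, and that a strict-order calculation describes a procedure the no-repeat rule excludes. This also stands. The 41% for a new participant's first lesion is therefore conditional, whereas the within-sequence figures need only consecutive use of a sequence.

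A reader might go further and infer that the operator recruits, judges eligibility and books visits. The documents say only that the operator informs patients; screening and enrolment are assigned to no one. Likewise, the envelopes are said to be available to the operator, which is not quite a statement of custody.

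**Conclusion.** The weakness in concealment is real. Under consecutive use of a sequence, the arm can be guessed 40.8% of the time against 16.7%, the mode 68.3% against 50%, and the sixth arm with certainty. These figures follow exactly from the stated list and from one operator seeing every assignment. Extension to a new participant's first lesion rests on carry-over, which the 210-envelope arithmetic implies unless every participant has six lesions. Without carry-over, the problem is confined to later lesions in the same mouth.

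A reader might want to turn predictability into an expected imbalance in difficult lesions. That would need the share of difficult lesions and how strongly the operator acts on a guess, and the documents give neither. The size of any bias cannot be computed, and nothing shows that steering would occur. The change is worth making because it is cheap, not because bias has been demonstrated.

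**What to change.** Amend section 2.2 so that the operator holds no pre-built envelopes:

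1. After consent and the pre-treatment assessment that section 2.5 places one week before restoration, the operator sends the participant's final list of included teeth to the statistical investigator.
2. From then on, no tooth is added or withdrawn because of allocation.
3. The statistical investigator returns the arms for all of that participant's teeth at once, drawn at random without repetition within the participant.
4. Balance towards 35 per arm is kept over the whole trial by weighting the draws to under-filled arms, in place of fixed blocks of six.

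This also settles which tooth takes which arm, satisfies the no-repeat rule, and leaves no leftover envelopes to handle.

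The cost is a wording change and one message per participant within the existing one-week gap, to a person the plan already contacts when more than six teeth qualify. No extra staff, visits or participants are needed for the procedure itself. There are two downsides. Arm totals may end slightly off 35, typically by one or two; because section 2.8 calls 35 a minimum, the amendment should say whether a small shortfall is accepted or made up. Some predictability also remains, mostly late in recruitment: with draws weighted by remaining places, simulation puts the average first-arm guess at about 22 to 23%, above the 16.7% of simple randomisation but well below 40.8%.
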